3.1.1. Retreatment

Retreatment of subjects who have progressed on LV monotherapy (Part A, Part B, and Part C Arm 1) or LV plus pembrolizumab (Part C Arm 2 and Arm 3) is not permitted.

3.2. Discussion and Rationale for Study Design

3.2.1. Rationale for Not Selecting Subjects Based Upon Detectable LIV-1 Protein Expression

LIV-1 is expressed in a variety of solid tumors (Section 1.1). LIV-1 expression is detected in the majority of breast cancer subtypes including TNBC (Modi 2018; Yau 2019). An IHC assay for LIV-1 showed that >90% of subjects treated with LV in the phase 1 study of LV monotherapy in mBC had a detectable level of LIV-1. Preliminary analyses comparing the magnitude of LIV-1 expression with response to LV in 2 independent cohorts of the phase 1 study did not show conclusive correlation between LIV-1 expression by IHC and response. To date, 5 out of 15 subjects that tested negative for LIV-1 expression by IHC assay have responded to LV, including 1 of 3 subjects with no detectable LIV-1 (Seagen Inc., data on file).

Biomarker assessments will not be used for subject selection as it is currently not known if expression of LIV-1 or other biomarkers will impact treatment outcome. Based on the experience of LV in mBC as described in Section 1.2.4, LV activity may not be limited to LIV-1 expressing tumors or diminish in the absence of LIV-1 expression. However, in order to understand relationships between the biological characteristics of the tumors chosen for study and subject outcome, pretreatment tumor biopsies will be collected and used for retrospective biomarker assessments.

3.2.2. Rationale for Selection of q3wk LV Dose

LV will be administered at 2.5 mg/kg (maximum dose of 250 mg per infusion) on Day 1 of each 21-day cycle in this open-label study. Dosing is based on the subject's actual body weight, measured at the beginning of each cycle. For subjects weighing >100 kg, dosing will be based on a 100 kg maximum weight (calculated dose not to exceed 250 mg per infusion).

This dose and regimen has been tested in 113 subjects with mBC, including LA/mTNBC, to date, including as 2L treatment in 47 subjects with LA/mTNBC. The regimen has been well tolerated, demonstrating an acceptable safety profile and encouraging clinical activity in the phase 1 study SGNLVA-001 (see Section 1.2.4).

Increasing antitumor activity was observed with increasing dose levels of LV in heavily pretreated LA/mTNBC patients. Confirmed PR, disease control rate (DCR), and median duration of response (DOR) were higher in the 2.5 mg/kg dose level compared to the 2.0 mg/kg dose level.

However, in the 2.5 mg/kg dose cohort, the incidence of neutropenia (Grade ≥ 3), including febrile neutropenia and serious neutropenia, was higher, particularly at doses >200 mg per infusion. Five of 11 subjects treated at >200 mg experienced SAEs associated with neutropenia. Febrile neutropenia occurred in 2 of 11 subjects, including 1 treatment-related death due to sepsis. No other treatment-related deaths occurred on study. Dose modifications due to AEs were more common at 2.5 mg/kg when receiving >200 mg. In contrast, there were no reported cases of febrile neutropenia or neutropenia associated SAEs in 18 subjects dosed at 2.5 mg/kg when receiving <200 mg.

Therefore, a recommended phase 2 dose of 2.5 mg/kg with a dose cap of 250 mg per infusion was selected, with subjects treated at a >200 mg dose per infusion required to receive prophylactic myeloid growth factor support (eg, granulocyte-colony stimulating factor [G-CSF]) to reduce the rate, severity, and complications of neutropenia, while maintaining the potential for responses.

3.2.3. Rationale for Mandatory G-CSF for Subjects Receiving More than 200 mg LV per Infusion in Part A

As described in Section 3.2.2, evaluation of the 2.5 mg/kg dose indicated that febrile neutropenia was observed more frequently at a dose of 2.5 mg/kg when the total dose was >200 mg than when the total dose was ≤ 200 mg per infusion (Modi 2018). Thus, subjects who receive a dose of LV >200 mg per infusion will be required to receive prophylactic G-CSF support to reduce the rate, severity, and complications of neutropenia. A recent evaluation demonstrates that primary prophylactic G-CSF has reduced the rate of treatment emergent neutropenia, postbaseline decreased absolute neutrophil count (ANC), and neutropenic infections in subjects receiving 2.5 mg/kg >200 mg LV (Seagen Inc., data on file).

3.2.4. Rationale for Selection of q1wk LV Doses

Multiple lines of evidence support that q1wk dosing may result in improved efficacy and safety of LV.

The starting weekly dose of LV in Part B of SGNLVA-005 will be 1.0 mg/kg (Dose Level 0). This LV dose results in a pharmacokinetic area-under-the-curve (AUC) exposure similar to LV of 2.5 mg/kg q3wk. At these similar pharmacokinetic exposures, it is not anticipated that there will be a detriment in the clinical efficacy or safety profile. As described in Section 1.2.4.3, LV has been shown to be tolerable and without any DLTs up to 1.5 mg/kg/week. The safety profile of LV q1wk appears safe and tolerable, with most TEAEs being Grade 1–2 in severity.

Further, while gastrointestinal toxicities (nausea, constipation, diarrhea, and vomiting) were among frequent AEs reported in subjects dosed with LV q3wk (Part A, B, C, and D of the study), LV q1wk appears to result in a numerically lower frequency of gastrointestinal toxicities compared to LV q3wk (Table 1 and Table 2).

In addition, preliminary data indicated that tumor size reductions in breast cancer patients were observed at the lowest dose level evaluated (1.0 mg/kg/week) with increased activity observed at 1.25 mg/kg q1wk (Seagen Inc., data on file).

Pharmacokinetic modeling data derived from over 200 subjects previously treated with LV q3wk suggest improvements in the safety profile of LV q1wk dosing may be due in part to the reduced

maximum concentration (C_{\max}) compared to q3wk dosing (Seagen Inc., data on file). In addition, LV q1wk dosing is anticipated to result in higher trough concentration (C_{trough}) levels (the lowest concentration reached by a drug before the next dose is administered), which are correlated with improved efficacy.

Other ADCs have been shown to have improved safety, activity, or both when administered at different doses and more frequent regimens than those originally tested. For example, trastuzumab emtansine (T-DM1), has improved efficacy with similar safety profiles when dosed q1wk compared to q3wk (Beeram 2012) (Thuss-Patience 2017).

3.2.5. Rationale for Selection of 2q3wk LV Dose (Part C)

LV monotherapy has been extensively evaluated across a range of doses and schedules in subjects with mBC in the concurrently ongoing phase 1 study SGNLVA-001 (see Section 1.2.4.3). In Part E of this study, 81 patients with mBC received LV administered at 1.0, 1.25, or 1.5 mg/kg weekly (q1wk). No DLTs were observed at any of the 3 starting doses evaluated in the dose escalation phase (Seagen Inc., data on file).

Preliminary efficacy results from Part E of the SGNLVA-001 study are shown in Figure 1 in Section 1.2.4.4 (data cut 06-Jan-2021). There appears to be greater magnitude of tumor size reduction with increasing dose of LV q1wk with the 1.5 mg/kg dose having the highest proportion of patients with measurable response. However, the frequency of AEs generally appears to increase with increasing dose as well. Table 2 in Section 1.2.4.3 summarizes the most commonly reported AEs by dose in SGNLVA-001 (26-July-2021, Seagen Inc., data on file). Due to the high frequency of neutropenia at the LV 1.5 mg/kg q1wk dose, (67% of patients with 44% of patients having Grade ≥ 3), accrual to this expansion cohort was paused. Although higher efficacy had been observed with the 1.5 mg/kg dose level, the better safety and tolerability of the 1.25 mg/kg dose led to further expansion of this cohort.

In the patients treated with LV monotherapy at the 1.25 mg/kg q1wk dose level, the relative dose intensity started to decrease by Cycle 2 (C2) leading to 2 doses being administered in every 3-week cycle. Similarly, most of the clinically significant neutropenia events in the 1.5 mg/kg dose level occurred after 3 weekly doses. Overall, these observations suggested that an LV drug holiday may be needed to mitigate AEs, including neutropenia, for long-term treatment. This is further supported by PK simulation which demonstrated that giving LV 1.5 mg/kg on Days 1 and 8 every 21 days (2q3wk) would result in similar PK exposures as 1.25 mg/kg q1wk dosing schedule. Based on this rationale, the intermittent dosing schedule of LV 1.5 mg/kg 2q3wk is being explored as monotherapy in Part F of study SGNLVA-001.

Additionally, efficacy results from Part C of study SGNLVA-002 evaluating LV at the 1.25 mg/kg q1wk dose level in combination with pembrolizumab q3wk as frontline therapy in patients with LA/mTNBC showed encouraging activity in both PD-L1 high and low/negative disease. Confirmed objective responses were observed in 46% of patients, respectively, with 3 patients (8%) having PD-L1 low/negative disease achieving a CR following treatment with the combination (Seagen Inc., data on file). However, frequent LV dose modifications were observed at the weekly dosing schedule which suggested that treatment holidays may be required for long-term dosing. Part D of study SGNLVA-002 is exploring the intermittent dosing schedule of LV 1.5 mg/kg 2q3wk in combination with pembrolizumab as 1L treatment in patients with PD-L1 low/negative LA/mTNBC (see Section 1.3.3.1).

In the current study SGNLVA-005, LV monotherapy has only been explored at the 1.25 mg/kg q1wk dosing schedule in patients with melanoma (Part B; Cohort 8). Interim results from this cohort showed preliminary signs of activity in this patient population, and the cohort was subsequently opened for expansion according to the prespecified protocol futility analysis criteria. Similar to what was observed in mBC, recent PK modeling based on the first 15 patients enrolled in Cohort 8 treated at the 1.25 mg/kg q1wk dose level also supports further evaluation of the LV 1.5 mg/kg 2q3wk schedule (Seagen Inc., data on file) to improve the overall safety profile and response durability in subjects with advanced melanoma.

3.2.6. Rationale for Combining LV with Pembrolizumab in Part C

Accumulating data suggests chemotherapeutic agents may activate the immune system by inducing tumor cell apoptosis and tumor-associated antigen release, a process termed ICD (Bracci 2014). Tumor-associated antigens are taken up by antigen presenting cells such as dendritic cells or macrophages which then traffic to tumor-draining lymph nodes and activate effector immune cells such as T-cells and natural killer (NK) cells. Activation and infiltration of these immune cells to the TME leads to a potent anti-tumor response.

LV and PD(L)1 inhibitors act through distinct but complementary mechanisms of action. Data from preclinical studies of MMAE ADCs comprising the same linker and MMAE payload as LV, brentuximab vedotin (a CD30-directed ADC) and enfortumab vedotin (a nectin-4 directed ADC), showed potential to induce ICD, antigen presentation, and tumor immune infiltration (Gardai 2015; Liu 2020). These results suggest that the effects are due to the MMAE payload (Gardai 2015; Liu 2020). These ADCs induce hallmarks of ICD with innate immune cell migration and activate adaptive immune response within the TME (Cao 2017; Cao 2018). The addition of immune checkpoint inhibitors, such as a PD(L)1 inhibitor like pembrolizumab, to treatment with MMAE conjugated ADCs can further amplify the adaptive immune response by preventing T-cell exhaustion and loss of inflammatory effector functions, as well as increasing T-cell and NK cell trafficking to the TME (Stagg 2011; Muller 2014; Muller 2015; Huang 2022).

A preliminary report using IHC and gene expression data from SGNLVA-001 and SGNLVA-002 studies that compared LV monotherapy to LV combined with pembrolizumab in subjects with LA/mTNBC showed that when subjects received both LV and pembrolizumab, there was evidence of enhanced immune activation in the TME. This included activation of adaptive immune response pathways and increased infiltration of CD8 T-cells in addition to macrophages (Pusztai 2020).

The antitumor immune response patterns seen with combining immunotherapeutic agents, such as pembrolizumab and LV, may extend beyond the typical time course of responses seen with cytotoxic agents and can manifest a clinical response after an initial increase in tumor burden or even the appearance of new lesions. Standard RECIST criteria may therefore not provide an accurate assessment of disease progression for immunotherapeutic agents. Therefore, in addition to RECIST v1.1, iRECIST will be used by study sites to evaluate disease progression for determining eligibility of treatment continuation in Part C (Arms 2 and 3) to account for the appearance of possible new lesions and allow radiographic progression to be confirmed at a subsequent assessment (see [Appendix I](#)).

3.2.7. Rationale for Pembrolizumab Dose

The planned dose of pembrolizumab for this study is 200 mg q3wk. Based on the totality of data generated in the Keytruda development program, 200 mg q3wk is an appropriate dose of pembrolizumab for adults across all indications. As outlined below, this dose is justified by:

- Clinical data from 8 randomized studies in melanoma and NSCLC indications demonstrating flat dose- and exposure-efficacy relationships from 2 mg/kg q3wk to 10 mg/kg every 2 weeks (q2wk) representing an approximate 5- to 7.5-fold exposure range (refer to the IB)
- Population PK analysis showing that both fixed dosing and weight-based dosing provides similar control of PK variability with considerable overlap in the distributions of exposures, supporting suitability of 200 mg q3wk
- Clinical data showing meaningful improvement in benefit-risk including overall survival (OS) at 200 mg q3wk across multiple indications, and
- Pharmacology data showing full target saturation in both systemic circulation (inferred from PK data) and tumor (inferred from physiologically-based PK [PBPK] analysis) at 200 mg q3wk.

Among the 8 randomized dose-comparison studies, a total of 2262 participants were enrolled with melanoma and NSCLC, covering different disease settings (treatment naïve, previously treated, PD-L1 enriched, and all-comers) and different treatment settings (monotherapy and in combination with chemotherapy). Five studies compared 2 mg/kg q3wk versus 10 mg/kg q2wk (KN001 Cohort B2, KN001 Cohort D, KN002, KN010, and KN021), and 3 studies compared 10 mg/kg q3wk versus 10 mg/kg q2wk (KN001 Cohort B3, KN001 Cohort F2 and KN006). All of these studies demonstrated flat dose- and exposure-response relationships across the doses studied representing an approximate 5- to 7.5-fold difference in exposure. The 2 mg/kg (or 200 mg fixed-dose) q3wk provided similar responses to the highest doses studied. Subsequently, flat dose- and exposure-response relationships were also observed in other tumor types including head and neck cancer, bladder cancer, gastric cancer, and classical Hodgkin Lymphoma, confirming 200 mg q3wk as the appropriate dose independent of the tumor type. These findings are consistent with the mechanism of action of pembrolizumab, which acts by interaction with immune cells, and not via direct binding to cancer cells.

Additionally, pharmacology data clearly show target saturation at 200 mg q3wk. First, PK data in KN001 evaluating target-mediated drug disposition conclusively demonstrated saturation of PD-1 in systemic circulation at doses much lower than 200 mg q3wk. Second, a PBPK analysis was conducted to predict tumor PD-1 saturation over a wide range of tumor penetration and PD-1 expression. This evaluation concluded that pembrolizumab at 200 mg q3wk achieves full PD-1 saturation in both blood and tumor.

Finally, population PK analysis of pembrolizumab, which characterized the influence of body weight and other participant covariates on exposure, has shown that the fixed-dosing provides similar control of PK variability as weight-based dosing, with considerable overlap in the distribution of exposures from the 200 mg q3wk fixed-dose and 2 mg/kg q3wk dose. Supported by these PK characteristics and given that fixed-dose has advantages of reduced dosing

complexity and reduced potential of dosing errors, the 200 mg q3wk fixed-dose was selected for evaluation across all pembrolizumab protocols.

3.2.8. Blinding and Unblinding

This is an open-label study.

4. STUDY POPULATION

Subjects must meet all enrollment criteria to be eligible for this study. Eligibility criteria may not be waived by the investigator and are subject to review in the event of a good clinical practice audit and/or health regulatory authority inspection.

4.1. Inclusion Criteria

Eligibility for each of the solid tumor cohorts are listed below:

- Cohort 1, SCLC (Part A and Part B):
 - Subjects must have pathologically-documented SCLC;
 - Must have extensive stage disease;
 - Must have disease progression during or following prior platinum-based systemic chemotherapy for extensive stage disease;
 - No more than 1 prior line of cytotoxic chemotherapy for extensive disease stage;
 - May have received prior anti-PD(L)1 therapy, unless contraindicated.
 - Mixed SCLC/neuroendocrine tumors with NSCLC histologies are not eligible.
- Cohort 2, NSCLC-squamous (Part A and Part B):
 - Must have pathologically-documented squamous cell NSCLC;
 - Must have unresectable locally advanced or metastatic disease;
 - Must have disease progression during or following systemic therapy:
 - Subjects must have progressed during or after a platinum-based combination therapy administered for the treatment of metastatic disease. Maintenance therapy is permitted provided there was no progression after the initial platinum-based combination. Changing chemotherapy agents during platinum-based treatment for the management of toxicities is permitted provided no progression has occurred while on the initial therapy; or
 - Subjects must have progressed within 6 months of last dose of platinum-based adjuvant, neoadjuvant, or definitive chemotherapy, or concomitant chemoradiation regimen for early stage or locally advanced stage disease.
 - Subjects with known epidermal growth factor receptor (EGFR), anaplastic lymphoma kinase (ALK), reactive oxygen species (ROS), BRAF, or other actionable mutations are not eligible;
 - No more than 1 prior line of cytotoxic chemotherapy for their advanced disease;
 - Must have received prior anti-PD(L)1 therapy, unless contraindicated;

- Subjects with mixed histology NSCLC are eligible as long as the tumor is predominantly squamous histology. Mixed SCLC/neuroendocrine tumors with NSCLC histologies are not eligible.
- Cohort 3, NSCLC–nonsquamous (Part A and Part B):
 - Must have pathologically-documented nonsquamous NSCLC;
 - Must have unresectable locally advanced or metastatic disease;
 - Must have disease progression during or following systemic therapy;
 - Subjects must have progressed during or after a platinum-based combination therapy administered for the treatment of metastatic disease. Maintenance therapy is permitted provided there was no progression after the initial platinum-based combination. Changing chemotherapy agents during platinum-based treatment for the management of toxicities is permitted provided no progression has occurred while on the initial therapy; or
 - Subjects must have progressed within 6 months of last dose of platinum-based adjuvant, neoadjuvant, or definitive chemotherapy, or concomitant chemoradiation regimen for early stage or locally advanced stage disease.
 - Subjects with known EGFR, ALK, ROS, BRAF, tropomyosin receptor kinase (TRK), or other actionable mutations are not eligible.
 - Must have had prior platinum-based chemotherapy;
 - No more than 1 prior line of cytotoxic chemotherapy for their advanced disease;
 - Must have received prior anti-PD(L)1 therapy, unless contraindicated;
 - Mixed tumors will be categorized by the predominant cell type. Subject is ineligible if the subject has predominantly squamous cell histology NSCLC or if small cell elements are present.
- Cohort 4, HNSCC (Part A and Part B):
 - Must have pathologically-documented squamous cell carcinoma of the head and neck with primary tumor site arising from the oral cavity, oropharynx, hypopharynx, and larynx; tumors arising from the nasopharynx are excluded.
 - Must have unresectable locally recurrent or metastatic disease;
 - Must have disease progression during or following prior line of systemic therapy;
 - Disease progression after treatment with a platinum-containing regimen for recurrent (disease not amenable to curative treatment)/metastatic disease; or

- Recurrence/progression within 6 months of last dose of platinum therapy given as part of multimodal therapy in the curative setting (eg locally advanced stage)
 - No more than 1 line of cytotoxic chemotherapy for their advanced disease;
 - May have received prior anti-PD(L)1 therapy, unless contraindicated.
- Cohort 5, esophageal-squamous (Part A and Part B):
 - Must have pathologically-documented squamous cell carcinoma of the esophagus;
 - Must have unresectable locally advanced or metastatic disease;
 - Must have disease progression during or following systemic therapy;
 - Must have had prior platinum-based chemotherapy;
 - No more than 1 line of cytotoxic chemotherapy for their advanced disease.
- Cohort 6, gastric and GEJ adenocarcinoma (Part A and Part B):
 - Must have pathologically-documented gastric or GEJ adenocarcinoma;
 - Must have unresectable locally advanced or metastatic disease;
 - Must have received prior platinum-based therapy;
 - Must have disease progression during or following systemic therapy;
 - Subjects with known human epidermal growth factor receptor 2 (HER2) overexpression must have received prior HER2-targeted therapy;
 - No more than 1 line of prior cytotoxic chemotherapy for their advanced disease;
 - Subjects may have received prior anti-PD(L)1 therapy, unless contraindicated.
- Cohort 7, CRPC (Part B only):
 - Must have histologically or cytologically confirmed adenocarcinoma of the prostate:
 - Subjects with components of small cell or neuroendocrine histology are excluded.
 - Must have metastatic castration-resistant disease:
 - Castration-resistant is defined as progressive disease following adequate medical or surgical (bilateral orchiectomy) castration and testosterone <50 ng/dL (<2.0 nM).
 - Must have been ≥28 days between cessation of androgen receptor-targeted therapy and start of study treatment;
 - Must have received no more than 1 prior line of 2nd generation androgen receptor-targeted therapy (eg, abiraterone acetate, enzalutamide, apalutamide,

- or darolutamide) for metastatic castration-sensitive prostate cancer (CSPC) or CRPC;
- No prior cytotoxic chemotherapy in the metastatic CRPC setting:
 - For subjects who received cytotoxic chemotherapy for CSPC, at least 6 months must have elapsed between last dose of chemotherapy and start of study treatment;
 - No more than 1 prior line of cytotoxic chemotherapy for CSPC
- Subjects with measurable and non-measurable disease are eligible if the following criteria are met:
 - A minimum starting PSA level ≥ 1.0 ng/mL;
 - Subjects with measurable soft tissue disease must have evidence of measurable soft tissue disease according to PCWG3 criteria. Previously normal (<1.0 cm) lymph nodes must have grown by ≥ 5 mm in the short axis to be considered to have progressed;
 - Subjects with nonmeasurable- disease (enrollment after interim analysis and no more than 15 subjects in total) must have documented rising PSA levels or appearance of new lesion according to PCWG3 ([Appendix L](#)):
 - PSA progression as defined by 2 increases in PSA level over a previous reference value (a minimum of 3 PSA values total) with an interval of ≥ 1 week between each assessment where the PSA value at screening should be ≥ 1 ng/mL, OR
 - Bone disease progression defined by 2 or more new lesions on bone scan
 - Subjects with known breast cancer gene (BRCA) mutations are excluded;
 - No prior radioisotope therapy or radiotherapy to $\geq 30\%$ of bone marrow.
- Cohort 8, melanoma (Part B and Part C):
 - Must have histologically or cytologically confirmed cutaneous malignant melanoma;
 - Subjects with mucosal, acral, or uveal melanoma are excluded.
 - Must have locally advanced unresectable or metastatic stage disease;
 - Must have measurable disease:
 - Lesions that have had prior intralesional therapies including talimogene laherparepvec (T-VEC) are not considered measurable;
 - Subjects with metastases limited to the skin (skin-only metastasis) are excluded.
 - Must have progressive disease following anti-PD(L)1 therapy;
 - No prior cytotoxic chemotherapy in the advanced disease setting;

- No more than 2 prior systemic therapies for advanced disease:
 - Adjuvant therapy within 6 months of diagnosis of advanced disease is considered as 1 line of therapy.
 - Prior anti-CTLA4 therapy is allowed;
 - Prior BRAF +/- mitogen-activated protein kinase (MEK) inhibitor therapy:
 - Part B subjects: May have received BRAF +/- MEK inhibitor therapy if BRAF mutated;
 - Part C subjects: Must have received BRAF +/- MEK inhibitor therapy if BRAF mutated

Inclusion criteria for Parts A, B, and C:

1. Measurable disease according to RECIST v1.1 ([Appendix H](#)) as assessed by the investigator
 - A minimum of one non-nodal lesion ≥ 10 mm in the longest diameter from a non-irradiated area
Or
 - Lymph node lesion ≥ 15 mm in the shortest diameter from a non-irradiated area
 - If target lesion(s) are located within previously irradiated area only, the subject can be enrolled only if there has been demonstrated progression in the “in field” lesion and upon approval of the sponsor’s medical monitor.
2. Age of at least 18 years, or legal age according to local regulations, whichever is older.
3. An Eastern Cooperative Oncology Group (ECOG) Performance Status score of 0 or 1 (see [Appendix J](#) for conversion of performance status using Karnofsky and Lansky scales, if applicable)
4. The following baseline laboratory data:
 - ANC $\geq 1500/\mu\text{L}$ assessed at least 2 weeks after growth factor support, if applicable
 - platelet count $\geq 100 \times 10^9/\text{L}$ assessed at least 2 weeks after transfusion with blood products, if applicable
 - hemoglobin ($\geq 8.0 \text{ g/dL}$) assessed at least 2 weeks after transfusion with blood products and/or growth factor support, if applicable
 - serum bilirubin $\leq 1.5 \times$ upper limit of normal (ULN) or direct bilirubin $\leq 3 \times$ ULN in subjects diagnosed with Gilbert’s syndrome
 - estimated glomerular filtration rate (GFR) $\geq 30 \text{ mL/min}/1.73 \text{ m}^2$ using the Modification of Diet in Renal Disease (MDRD) study equation as applicable (see Section [7.6.3](#))
 - alanine aminotransferase (ALT) and aspartate aminotransferase (AST) $\leq 1.5 \times$ ULN (if liver metastases are present, then $\leq 3 \times$ ULN is allowed)

5. Subjects of childbearing potential as defined in Section 4.3, under the following conditions:
 - Must have a negative serum or urine pregnancy test (minimum sensitivity 25 mIU/mL or equivalent units of beta human chorionic gonadotropin [β -hCG]) result within 3 days prior to the first dose of LV. Subjects with false positive results and documented verification that the subject is not pregnant are eligible for participation.
 - Must agree not to try to become pregnant during the study and for at least 6 months after the final dose of study drug administration
 - Must agree not to breastfeed or donate ova, starting at time of informed consent and continuing through 6 months after the final dose of study drug administration
 - If sexually active in a way that could lead to pregnancy, must consistently use 2 highly effective methods of birth control (as defined in [Appendix K](#)) starting at time of informed consent and continuing throughout the study and for at least 6 months after the final dose of study drug administration
6. Subjects who can father children, under the following conditions:
 - Must agree not to donate sperm starting at time of informed consent and continuing throughout the study period and for at least 6 months after the final study drug administration
 - If sexually active with a subject of childbearing potential in a way that could lead to pregnancy, must consistently use 2 highly effective methods of birth control (as defined in [Appendix K](#)) starting at time of informed consent and continuing throughout the study and for at least 6 months after the final dose of study drug administration
 - If sexually active with a subject who is pregnant or breastfeeding, must consistently use one of 2 contraception options (as defined in [Appendix K](#)) starting at time of informed consent and continuing throughout the study and for at least 6 months after the final dose of study drug administration
7. Available and adequate archival baseline tumor sample is required. If an archival baseline tumor sample is not available, a fresh biopsy sample may be submitted if medically feasible or the medical monitor should be contacted to review this requirement. Formalin fixed paraffin embedded (FFPE) blocks and core needle or excisional biopsy of metastatic site are preferred.
8. The subject or the subject's legally authorized representative must provide written informed consent.

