7.6.3. Clinical Laboratory Tests

The following safety laboratory assessments will be performed by local laboratories at the designated time points (see [Appendix A](#), [Appendix B](#), [Appendix C](#), and [Appendix D](#)) during the course of the study. Results of all clinical laboratory tests except pregnancy and PSA tests are to be submitted to iRIS. Instructions for submission to iRIS are located in the iRIS Manual.

- Serum chemistry panel: including sodium, potassium, blood urea nitrogen/blood urea, creatinine, calcium, albumin, and magnesium.
- Liver function tests including total bilirubin, alkaline phosphatase, ALT, and AST
- CBC with differential: white blood count, hemoglobin, hematocrit and platelets; and the differential including, but not limited to, neutrophils, lymphocytes, and monocytes
- PSA test (prostate cancer patients only)
- Testosterone measurement (at Screening, prostate cancer patients only)
- Blood glucose
 - Fasting blood glucose is only required at screening. If fasting blood glucose is elevated, a repeat assessment must be obtained.
- HbA1c: if HbA1c is elevated during screening, HbA1c assessment must be repeated to confirm
- The estimated GFR should be calculated using the MDRD equation as applicable, with serum creatinine (Scr) reported in mg/dL.

$$\text{GFR (mL/min/1.73 m}^2\text{)} = 175 \times (\text{Scr})^{-1.154} \times (\text{Age})^{-0.203} \times (0.742 \text{ if female}) \times (1.212 \text{ if African American})$$

- Thyroid function tests, including TSH, T3 or free T3, and free T4 (Part C Arm 2 and Arm 3).

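### The Cohort 7 castrate testosterone limit is printed as two unequal values: 50 ng/dL is 1.73 nM, not 2.0 nM

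*Protocol*

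**What the plan says.** Protocol Section 4.1 (Inclusion Criteria, Cohort 7) defines castration-resistant as progressive disease after adequate medical or surgical "castration and testosterone <50 ng/dL (<2.0 nM"). The molar value stands in parentheses after the mass value, which is how the same limit is shown in a second unit.

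The opening of Protocol Section 4 makes the criteria binding: "Eligibility criteria may not be waived by the investigator", and they are open to review at audit or inspection.

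Protocol Section 7.6.3 lists "Testosterone measurement (at Screening, prostate cancer patients only") among its tests and says of the list: "The following safety laboratory assessments will be performed by local laboratories at the designated time points". Section 6.3.1 and Appendix A also place the test at screening. Section 3.1 describes the trial as global. Results go to iRIS under a manual that is not among the documents. Appendix C requires eligibility confirmation to be sent to the sponsor before treatment.

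Neither document gives a reporting unit for testosterone, a conversion factor, or a statement of which figure takes precedence. The SAP was written for the original protocol and covers Cohorts 1 to 6. It mentions neither Cohort 7 nor testosterone.

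**The concern.** A limit printed in two units should admit the same people whichever unit is read. Here the molar figure is the looser one. The same serum level can then be compliant when reported in nM and an eligibility breach when reported in ng/dL, and a monitor has no text for deciding which reading is right.

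What is at stake is uniform application of the criterion that decides who belongs in Cohort 7, a cohort in which confirmed PSA response is a primary endpoint alongside ORR (Protocol Sections 2 and 9.3.5.1).

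**Working it through.** **Inputs**

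- Mass limit: 50 ng/dL (Protocol 4.1).
- Molar limit: 2.0 nM (Protocol 4.1).
- Molar mass of testosterone, C19H28O2. The documents do not give it, so it is an assumption computed from atomic masses: 19 × 12.011 + 28 × 1.008 + 2 × 15.999 = 288.43 g/mol. It is used as 288.4 and varied from 288 to 289.

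**Trying to reproduce the printed equivalent**

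The formula is nM = (ng/dL × 10) / molar mass.

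- 50 ng/dL = 500 ng/L, and 500 / 288.4 = 1.73 nM. Over molar masses 289 to 288 the result is 1.730 to 1.736 nM.
- The printed figure is 2.0 nM, so it is not reproduced.

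**The reverse direction**

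The formula is ng/dL = nM × molar mass / 10.

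- 2.0 × 288.4 / 10 = 57.7 ng/dL (57.6 to 57.8 over the range).
- Ratio of the two limits: 57.7 / 50 = 1.154. The molar limit is about 15% higher (15.2% to 15.6% over the range).
- The two figures would agree only at a molar mass of 500 / 2.0 = 250 g/mol, far from any rounding of the true value.

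**Could rounding explain it?**

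The protocol prints one decimal. At one decimal, 1.73 becomes 1.7. From the other side, the smallest value that rounds to 2.0 is 1.95 nM, which is 1.95 × 288.4 / 10 = 56.2 ng/dL, still above 50.

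**How the protocol's other paired units behave**

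Protocol Section 5.6 prints glucose limits in two units. With a molar mass of glucose of 180.2 g/mol (also an assumption), 250 mg/dL is 2500 / 180.2 = 13.9 mmol/L and 126 mg/dL is 1260 / 180.2 = 7.0 mmol/L. Both match the printed 13.9 and 7. True equivalents are the practice there, and the testosterone pair departs from it.

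**Who is affected**

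| Screening testosterone | Below 50 ng/dL? | Below 2.0 nM? |
|---|---|---|
| Under 50 ng/dL (under 1.73 nM) | Yes | Yes |
| 1.8 nM = 51.9 ng/dL | No | Yes |
| 1.9 nM = 54.8 ng/dL | No | Yes |
| 57.7 ng/dL (2.0 nM) or more | No | No |

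The limits disagree only from 50 to just under 57.7 ng/dL, a band 7.7 ng/dL wide. The documents give no testosterone distribution, so the number of subjects in it cannot be estimated.

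**Upper end of the effect on the endpoint**

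If one such subject were enrolled and also had a confirmed PSA response, the rate would move by 1/30 = 3.3 percentage points with 30 evaluable subjects. Cohort 7 enrols up to 30, and Section 9.3.5 uses the PSA evaluable set, so the denominator may be smaller and the step a little larger. For scale, Section 9.1 gives a 90% interval of 17% to 47% around an observed 30% in 30 subjects.

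**The case against.** The arithmetic is hard to dispute; the objections concern how much follows from it.

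**Use of both units is an inference.** The protocol says local laboratories and a global trial. It names no laboratory's reporting unit. The text supports only that both units may be used. This stands. The defect does not depend on it, because the criterion itself prints both limits.

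**The site does not act alone.** Eligibility confirmation goes to the sponsor before treatment, and testosterone results go to iRIS. Either step is a point at which one limit could be applied to everyone. This stands as mitigation. Nothing in the documents says that either step harmonises the unit, and the printed criterion stays inconsistent in any case.

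**The effect is small and conditional.** The 3.3-point shift needs a subject in a narrow band who is enrolled under the molar reading and is also a confirmed responder. No probability can be attached to that. Against the planned interval width, in a study without formal hypothesis testing, one subject matters little. This stands in full.

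**A stronger inference does not hold.** A reader might infer that an incompletely castrate subject could have a PSA fall from androgen suppression that is then credited to LV. The documents do not support this:

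- The Cohort 7 definition already requires progression after adequate castration, so unchanged suppression is an unlikely source of a new PSA fall.
- Cohort 7 subjects must be at least 28 days past androgen receptor-targeted therapy before starting.
- Section 5.4.4 prohibits endocrine therapy during treatment, so adding or tightening suppression is not allowed as written. The section does not say whether background castration is exempt.
- A PSA response needs a fall of at least 50%, measured twice at least 3 weeks apart.

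**Conclusion.** The point holds as a unit mismatch within one binding criterion. Section 4.1 gives a single testosterone limit as two values about 15% apart, and neither document says which one governs. A subject from 50 to just under 57.7 ng/dL (1.73 to just under 2.0 nM) passes one and fails the other.

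The only outside input is the molar mass of testosterone. The conclusion is the same throughout 288 to 289 g/mol, and rounding does not explain the gap.

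The practical weight is low. Few subjects are likely to fall in the band, although that is a judgement rather than a figure from the documents, and the effect on the PSA response rate is probably small. There is no basis here for saying that the PSA endpoint is biased. The error deserves correction because it sits in a criterion that cannot be waived and that defines the cohort. Which limit is clinically appropriate is not decided here.

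**What to change.** In Protocol Section 4.1, Cohort 7, the sponsor should decide which of the two printed figures governs and replace the other with its exact equivalent:

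- if the ng/dL figure governs, 50 ng/dL pairs with 1.73 nM;
- if the nM figure governs, 2.0 nM pairs with 57.7 ng/dL.

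Keep enough decimals that the mismatch does not return. For example, 1.7 nM is 1.7 × 288.4 / 10 = 49.0 ng/dL, whereas 1.73 nM is 49.9 ng/dL.

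Then list any enrolled Cohort 7 subject whose screening testosterone lies from 50 to just under 57.7 ng/dL, with the unit in which the laboratory reported it, so that eligibility can be judged against the governing figure.

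The cost is one corrected number and a short listing from screening results already collected. No new tests or visits are needed.
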